Ambulatory surgery is occurring with rapidly increasing frequency as surgical and anesthetic techniques have improved and pressure to reduce health-care costs has increased. While there are many benefits to recovering from surgery within the home, a significant disadvantage is the lack of rapid access to a healthcare provider when postoperative complications occur. Postoperative nausea and vomiting (PONV) are common after surgery and anesthesia, and recent studies have demonstrated a high incidence of post-discharge nausea and vomiting (PDNV) after ambulatory surgery, particularly in high-risk groups (female gender, age less than 50 years, history of PONV, opioid administration in the post-anesthesia care unit (PACU), and nausea in the PACU). Current practices known to reduce the risk of postoperative nausea and vomiting in the PACU, such as the avoidance of volatile anesthetics and the use of intraoperative ondansetron and steroids, have little effect on the risk of delayed PDNV. Novel strategies to prevent PDNV are needed. Orally administered olanzapine, which has been shown to decrease the incidence of chemotherapy-induced nausea and vomiting, demonstrates promise as a novel strategy for preventing PDNV. It has a long half-life, allowing for a single dose to be administered preoperatively. This study will evaluate whether there is a difference in the incidence and severity of PDNV between patients who receive oral olanzapine versus placebo prior to general anesthesia for ambulatory surgery.

1) Objectives:

	Protocol Title:	Olanzapine for the treatment of Post-Discharge Nausea and Vomiting after Ambulatory Surgery
	Principal Investigator Name/Contact Info:	[name] [contact]
	Primary Contact Name/Contact Info:	[name] [contact] [name] [contact]
	Date Revised:	1/31/2018
	Study Number:	GCO#15-1297; HSM# 15-00501

Research Question: Does the addition of olanzapine administered prior to anesthetic induction reduce the risk of PDNV within the first 24 hours after ambulatory surgery relative to placebo?

Primary Objective: Compare the rate of post-discharge nausea or retching/vomiting in patients who receive olanzapine versus placebo.

Secondary Objectives:

- a) Measure the rate of post-discharge retching/vomiting in patients who receive olanzapine versus placebo.
- b) Measure the rate of post-discharge nausea in patients who receive olanzapine versus placebo.
- c) Measure the severity of post-discharge nausea in patients who receive olanzapine versus placebo using an 11-point Likert scale.

2) Background

Postoperative nausea and vomiting (PONV) are common complications that cause significant patient distress and dissatisfaction. PONV can increase costs, delay postanesthesia care unit discharge, and result in unanticipated hospital admission. In rare cases, serious medical complications can result, including postoperative bleeding, esophageal rupture, and pneumothoraces.¹ The incidence of postoperative nausea is approximately 50% and the incidence of vomiting is 30%.² As a result of its frequent occurrence and associated complications, PONV is a commonly evaluated quality and safety indicator.³ The independent risk factors for PONV include female gender, history of PONV, non-smoking status, use of inhalational anesthetics, longer duration of anesthetic, use of postoperative opioids, and younger age.⁴

Ambulatory surgical procedures, which tend to be shorter in duration, are fortunately associated with less PONV in the recovery room. Recent studies however, have highlighted the magnitude of delayed post-discharge nausea and vomiting (PDNV). A large prospective multi-center study found a 37% incidence of PDNV after general anesthesia.¹ Given the rapidly increasing number of ambulatory surgical procedures performed, this amounts to 4.3 million patients with PDNV each year in the United States. Interestingly, only 20.7% of these patients suffered from PONV in the PACU prior to discharge. Most patients do not alert a healthcare provider when they suffer from nausea or vomiting after discharge, causing this frequent complication to remain under-

	Protocol Title:	Olanzapine for the treatment of Post-Discharge Nausea and Vomiting after Ambulatory Surgery
	Principal Investigator Name/Contact Info:	[name] [contact]
	Primary Contact Name/Contact Info:	[name] [contact] [name] [contact]
	Date Revised:	1/31/2018
	Study Number:	GCO#15-1297; HSM# 15-00501

recognized.⁵ PDNV can be significantly distressing to patients who are at home and no longer have access to intravenous antiemetic medication. Furthermore, patients who suffer from PDNV do not return to their normal daily activities until the nausea and vomiting have resolved.⁵

Independent predictors of PDNV include female gender, age less than 50 years, history of PONV, opioid administration in the PACU, and nausea in the PACU. A risk score for PDNV is based on these five factors.¹ Zero, one, two, three, four, and five of these factors are associated with a 7%, 20%, 28%, 53%, 60%, and 89% incidence of PDNV. Intraoperatively administered ondansetron, which has a half-life of approximately three hours, does not reduce the risk of PDNV. There is a trend toward decreased PDNV with intraoperative use of glucocorticoids, but the difference does not reach statistical significance. Avoidance of volatile anesthetics in favor of a total intravenous anesthetic technique (TIVA), which reduces PONV, does not affect the incidence of PDNV.⁶ Given the high incidence of PDNV and paucity of effective prevention strategies, novel approaches for preventing this common complication are needed.

Olanzapine, an atypical antipsychotic medication in the thienobenzodiazepine class, antagonizes several receptors implicated in the pathogenesis of nausea and vomiting and has promising potential for the prevention of PDNV. Specifically, olanzapine antagonizes dopamine (D₁, D₂, D₄), serotonin (5HT_{2A}, 5HT_{2C}, 5HT₃), alpha-1 adrenergic, histamine (H₁), and multiple muscarinic receptors.⁷ There is strong evidence for the antiemetic efficacy of olanzapine for both the prevention and treatment of chemotherapy induced nausea and vomiting (CINV).⁸ A phase I study showed a maximum tolerated dose of 5mg during the two days prior to chemotherapy and 10mg for the next 7 days. Two phase II studies demonstrated efficacy with a similar protocol.^{9,10}

Three randomized controlled phase III trials including 488 patients in total showed significant improvements in CINV prevention with antiemetic regimens that included olanzapine 10mg daily during treatment. Additionally, three randomized trials including a total of 323 patients showed efficacy for breakthrough CINV treatment with 10mg of olanzapine. Importantly, olanzapine was safe and well-tolerated in all trials without significant differences in adverse effects (including dizziness, sedation, and extrapyramidal symptoms) between treatment and control groups, although the majority of the studies were not double-blind. Long-term use of olanzapine is associated with weight gain, dyslipidemia, and increased risk of developing diabetes mellitus but these complications were not seen with short-term use for CINV prevention or treatment.⁸

To date, there is one small study examining the efficacy of olanzapine on the prevention

	Protocol Title:	Olanzapine for the treatment of Post-Discharge Nausea and Vomiting after Ambulatory Surgery
	Principal Investigator Name/Contact Info:	[name] [contact]
	Primary Contact Name/Contact Info:	[name] [contact] [name] [contact]
	Date Revised:	1/31/2018
	Study Number:	GCO#15-1297; HSM# 15-00501

of post-operative nausea and vomiting. The results are promising in that 57% of patients in the placebo group required rescue antiemetic medications in the first 24 hours after surgery, whereas 37% of patients who received 10mg of oral olanzapine required breakthrough medication. This study included 82 patients undergoing general anesthesia for breast surgery who were randomized to receive placebo, olanzapine 5mg, olanzapine 10mg, or ondansetron 16mg prior to surgery. Outcomes measured were emetic episodes and need for rescue medications. Olanzapine and ondansetron showed similar efficacy in reducing nausea and vomiting. There was a trend toward increased efficacy of olanzapine 10mg compared to 5mg, but this did not reach statistical significance. There was no difference in frequency of adverse events between groups, including sedation, anxiety, restlessness, abnormal muscle movement, and headache.¹¹

In the case of PDNV, the use of postoperative opioids is likely a significant contributory factor, as it occurs hours after the anesthetic agents have been metabolized. This is likely why the use of TIVA, which helps prevent PONV, has no effect on the incidence of PDNV. One mechanism of opioid-induced nausea and vomiting is mediated through D₂ receptors in the chemoreceptor trigger zone in the medulla oblongata.¹² This makes anti-dopaminergic agents, such as olanzapine, ideal to target opioid induced nausea and vomiting. The half-life elimination of orally administered olanzapine is 21-54 hours. The time to peak plasma concentration is approximately 6 hours. Therefore orally administered olanzapine, taken with a small sip of water prior to anesthetic induction, demonstrates ideal pharmacokinetics for the prevention of delayed PDNV. Olanzapine's long half-life, low cost, excellent safety profile with short-term use, and targeting of multiple receptors implicated in nausea and vomiting (especially D₂) make it a hopeful prospect for the prevention of PDNV.

3) Setting of the Human Research

This study will be conducted at the Icahn School of Medicine at Mount Sinai. Consent will be obtained at the Mount Sinai OB/GYN Ambulatory Department at [name] Klingenstein Pavilion E level clinic and OB/Gyn Mount Sinai Faculty Practice Associates (FPA) at [name]

Study medications will be administered in the preoperative holding area in the sixth floor of the Annenberg Pavilion at [name]. The intraoperative protocol will take place in the operating room in which the case is scheduled. An investigator will evaluate the patient postoperatively in the Annenberg sixth floor PACU.

4) Resources Available to Conduct the Human Research

	Protocol Title:	Olanzapine for the treatment of Post-Discharge Nausea and Vomiting after Ambulatory Surgery
	Principal Investigator Name/Contact Info:	[name] [contact]
	Primary Contact Name/Contact Info:	[name] [contact] [name] [contact]
	Date Revised:	1/31/2018
	Study Number:	GCO#15-1297; HSM# 15-00501

Prior to initiating this study, all participating investigators and support staff will conduct a protocol initiation meeting to ensure adequate knowledge of the study objectives, procedures, populations, and human subject protections. A log of meeting attendees will be maintained. The team of investigators includes anesthesiologists with expertise in anesthesia for ambulatory procedures, surgeons, and a biostatistician. A study physician will be available at all times for subjects to call regarding potential adverse effects related to the study drug.

The surgical co-investigators perform approximately 12 ambulatory surgical procedures requiring general anesthesia a week, and slightly less than half of those patients are less than 50 years old. By this estimation, there should be approximately 6 eligible patient per week, or 312 eligible patients in a year.

The Investigational Drug Service within the Mount Sinai Hospital Department of Pharmacy will be utilized to randomize consented patients to receive olanzapine versus placebo, and to supply the appropriate medication on the day of surgery.

5) Study Design

a) Recruitment Methods

Patients who consent to and are scheduled to undergo ambulatory surgery at Mount Sinai will be invited by their physician to participate in the study prior to the scheduled date of surgery at their routine preoperative visit at their physician's office. Office locations where recruitment will occur include: the Mount Sinai OB/GYN Ambulatory Department at 1 [REDACTED], the OB/Gyn Mount Sinai Faculty Practice Associates (FPA) at [REDACTED] Upper East Side Gynecology at [REDACTED], Gramercy Gynecology at [REDACTED], New York Physicians at [REDACTED], and the Plastic and Reconstructive Surgery Office at [REDACTED]. A flyer describing the study will be displayed at the first two clinic locations to advertise the study to potential participants. The flyer will instruct interested patients to discuss the study with their gynecologist, or to contact the principal investigator directly. If a patient tells their physician that they are willing to participate, a study investigator will describe the study in detail, answer questions, confirm participant understanding, and provide the written informed consent form for review. If the patient agrees, written informed consent will be obtained at this visit, with opportunity for the subject to withdraw at any time prior to the surgical procedure.

	Protocol Title:	Olanzapine for the treatment of Post-Discharge Nausea and Vomiting after Ambulatory Surgery
	Principal Investigator Name/Contact Info:	[name] [contact]
	Primary Contact Name/Contact Info:	[name] [contact] [name] [contact]
	Date Revised:	1/31/2018
	Study Number:	GCO#15-1297; HSM# 15-00501

b) Inclusion and Exclusion Criteria

Inclusion Criteria:

1. Adults age ≥ 18 and ≤ 50 years old
2. Patient scheduled to undergo ambulatory surgery under general anesthesia
3. Willing and able to provide informed consent

Exclusion Criteria:

1. Unable to swallow pills
2. Current use of typical or atypical anti-psychotic medications
3. History of allergy to olanzapine
4. Pregnancy/Lactation (subjects of child-bearing potential will have a urine pregnancy test performed the day of surgery)
5. History of QTcF > 450 ms or torsades de pointes
6. Current use of antihypertensive medication
7. Diabetes Mellitus
8. Clinically significant cardiovascular disease defined as follows:
 - a. Myocardial infarction or unstable angina within 6 months prior to the day of planned surgery.
 - b. History of serious ventricular arrhythmia (i.e.: ventricular tachycardia or ventricular fibrillation) or cardiac arrhythmias requiring anti-arrhythmic medications, except for atrial fibrillation that is well controlled on anti-arrhythmic medication.
 - c. New York Heart Association (NYHA) Class II or higher congestive heart failure.
9. Postural hypotension or vasovagal syncope within 6 months of planned surgery.

	Protocol Title:	Olanzapine for the treatment of Post-Discharge Nausea and Vomiting after Ambulatory Surgery
	Principal Investigator Name/Contact Info:	[name] [contact]
	Primary Contact Name/Contact Info:	[name] [contact] [name] [contact]
	Date Revised:	1/31/2018
	Study Number:	GCO#15-1297; HSM# 15-00501

10. Hypotension on day of surgery, defined as a systolic blood pressure < 90mm Hg or a diastolic pressure < 60mm Hg.
11. Seizure disorder
12. Clinically active prolactinoma
13. Hepatic disease
14. Poorly controlled diabetes
15. Pre-operative blood glucose > 250 mg/dL
16. Narrow angle glaucoma
17. Parkinson's disease
18. Lewy body dementia

c) Number of Subjects

The majority of PONV interventions in use in current clinical practice reduce the risk by approximately 20%. This reduction is additive when multiple interventions are used. Assuming a 37% incidence of PDNV based on previous literature, to be powered to find a 20% reduction in risk from baseline the study must include 140 patients.

d) Study Timelines

Patients who consent to and are scheduled to undergo ambulatory surgery at Mount Sinai will be invited by their physician to participate in the study prior to the scheduled date of surgery at their routine preoperative visit. If a patient expresses interest in the study after viewing the recruitment flyer, arrangement will be made for an investigator to meet with the patient in clinic prior to the scheduled surgery to explain the study, screen the patient for eligibility, and obtain consent if appropriate. Patients who are consented will be randomized prior to their planned surgery. They will be followed for postoperative nausea and vomiting for 24 hours after discharge by telephone call on post-operative day one.

	Protocol Title:	Olanzapine for the treatment of Post-Discharge Nausea and Vomiting after Ambulatory Surgery
	Principal Investigator Name/Contact Info:	[name] [contact]
	Primary Contact Name/Contact Info:	[name] [contact] [name] [contact]
	Date Revised:	1/31/2018
	Study Number:	GCO#15-1297; HSM# 15-00501

Based on the enrollment within the first year of the study, we expect to have 20-30 patients complete the study per year. Assuming that enrollment continues at the current pace, it will take approximately five years to enroll the necessary 140 patients. As patients only need to be followed for 24 hours after discharge to be assessed for all primary and secondary endpoints, we estimate the study will be complete within 2 weeks of final patient enrollment.

e) Study Endpoints

Primary Objective: Compare the rate of post-discharge retching/vomiting or nausea in patients who receive olanzapine versus placebo.

Secondary Objectives:

- i) Measure the rate of post-discharge retching/vomiting in patients who receive olanzapine versus placebo.
- ii) Measure the rate of post-discharge nausea in patients who receive olanzapine versus placebo.
- iii) Measure the severity of post-discharge nausea in patients who receive olanzapine versus placebo using an 11-point Likert scale.

f) Procedures Involved in the Human Research

Subjects who consent to and are scheduled for ambulatory surgery under general anesthesia will be invited to participate in the study during a routine preoperative visit prior to the day of surgery by a study investigator. The details of the study will be reviewed and written informed consent will be obtained. Additionally, a flyer describing the study will be displayed at the two participating clinic locations to advertise the study to potential participants. The flyer will instruct interested patients to discuss the study with their gynecologist, or to contact the principal investigator directly. If a patient tells their physician that they are willing to participate, a study investigator will describe the study in detail, answer questions, confirm participant understanding, and provide the written informed consent form for review. Patients who have agreed to participate will have a 12-lead electrocardiogram (EKG) obtained in pre-surgical testing. Alternatively, if an EKG is not obtained prior to the day of surgery, it will be performed the same day in the assessment area prior

	Protocol Title:	Olanzapine for the treatment of Post-Discharge Nausea and Vomiting after Ambulatory Surgery
	Principal Investigator Name/Contact Info:	[name] [contact]
	Primary Contact Name/Contact Info:	[name] [contact] [name] [contact]
	Date Revised:	1/31/2018
	Study Number:	GCO#15-1297; HSM# 15-00501

to surgery. Patient's with a QTc > 450 ms using the Fridericia formula will be excluded.

Subjects will be counseled verbally to avoid alcohol, benzodiazepines, and motor vehicle driving for 24 hours following discharge.

The name and date of surgery of the consenting patient will be given to the Investigational Drug Service of the Mount Sinai Pharmacy for randomization and preparation of the medication. On the day of surgery, an investigator will pick up the medication from the pharmacy for the individual subject, and have the subject take the medication with a small sip of water in the preoperative holding area within one hour prior to entering the operating room. In addition, the patient will be provided with a standardized diary to record episodes of vomiting for the first 24 hours after discharge and will be provided with verbal and written instructions for completing the diary (appendix 1). Subjects will be asked for a preferred contact number for the postoperative phone call and permission to leave a voicemail will be requested.

Upon entering the operating room, after application of standard monitors, midazolam 2 mg will be administered for anxiolysis. If endotracheal intubation is indicated, general anesthesia will be induced using fentanyl 3-5 mcg/kg and propofol 1.5-2.5 mg/kg and muscle relaxation achieved with succinylcholine 1-2 mg/kg or rocuronium 0.6 mg/kg, at the discretion of the attending anesthesiologist. Rocuronium will be administered as needed to maintain muscle relaxation during the case. If a laryngeal mask airway is to be used rather than an endotracheal tube, anesthesia will be induced with propofol 1.5-2.5 mg/kg. Regardless of method of airway management, anesthesia will be maintained with sevoflurane at concentrations deemed appropriate by the anesthesia provider based on intraoperative hemodynamic and respiratory monitoring. Additional doses fentanyl will be administered also as deemed appropriate by the anesthesia provider based on intraoperative hemodynamic and respiratory monitoring. All patients will receive dexamethasone 8 mg immediately following induction, and ondansetron 4 mg and ketorolac 30mg approximately 30 minutes prior to emergence from anesthesia unless there is a specific contraindication. Intubated patients will receive neuromuscular blockade reversal with neostigmine 0.4-0.7 mg/kg prior to tracheal extubation.

	Protocol Title:	Olanzapine for the treatment of Post-Discharge Nausea and Vomiting after Ambulatory Surgery
	Principal Investigator Name/Contact Info:	[name] [contact]
	Primary Contact Name/Contact Info:	[name] [contact] [name] [contact]
	Date Revised:	1/31/2018
	Study Number:	GCO#15-1297; HSM# 15-00501

In the PACU, as needed ondansetron will be ordered as per the department standard orderset, (ondansetron 4 mg intravenous every 4 hours). However, the standard prochlorperazine 10 mg intravenous once will be removed from the orderset to reduce the risk of neuroleptic malignant syndrome or extrapyramidal symptoms when administered in combination with olanzapine. The patients' experience of nausea and/or vomiting will be assessed at 30, 60, and 120 minutes after surgery by trained study personnel. PACU EPIC records will also be audited to record the need for rescue antiemetic medications.

Prior to discharge from the PACU, subjects will be assessed for signs of orthostatic hypotension (a decrease of 20 mmHg in systolic blood pressure or 10 mmHg in diastolic blood pressure upon standing). Patients who meet the criteria for orthostatic hypotension will be evaluated and treated with intravenous fluid administration. Upon discharge, patients who had symptoms of orthostatic hypotension will be instructed to ambulate with assistance for the first 24 hours after discharge.

Information entered into the subjects' diary will be obtained during a telephone interview on the afternoon or evening of the first day following surgery. At this time investigators will also screen for adverse events.

Relevant preoperative, intraoperative, and postoperative data will be obtained from the anesthesia record, the EPIC electronic medical record, and the telephone interviews and collected on standardized forms by trained study personnel.

Data to be collected:

Age
BMI
ASA status
Smoking status
History of PONV
History of motion sickness
Total intraoperative fentanyl (mcg)
Total intraoperative propofol (mg)
Total intraoperative rocuronium (mg)
Total intraoperative neostigmine (mg)
Total intraoperative Sevoflurane
Duration of surgery
Total fentanyl dose in PACU (mcg)

	Protocol Title:	Olanzapine for the treatment of Post-Discharge Nausea and Vomiting after Ambulatory Surgery
	Principal Investigator Name/Contact Info:	[name] [contact]
	Primary Contact Name/Contact Info:	[name] [contact] [name] [contact]
	Date Revised:	1/31/2018
	Study Number:	GCO#15-1297; HSM# 15-00501

Total oxycodone dose in PACU (mg)
Rescue antiemetics in PACU (yes/no)
Ondansetron total dose (mg)
Length of PACU stay (minutes)
Vomiting in PACU (#episodes at least 1 min apart)
Nausea in PACU (highest number reported on 11 point Likert scale)
Post-discharge vomiting (#episodes at least 1 minute apart)
Post-discharge nausea (highest number reported on 11 point Likert scale)

g) Specimen Banking

N/A

h) Data Management and Confidentiality

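### Section 5c: 140 patients give about 15% power (two-sided 5%) for a 20% reduction from 37% as worded; the number fits only a fall of 20 percentage points, which the plan does not state

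*Combined protocol and SAP*

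**What the plan says.** Section 5c bases the sample size on three statements. The first gives the rationale for the effect: "The majority of PONV interventions in use in current clinical practice reduce the risk by approximately 20" per cent. The second adds: "This reduction is additive when multiple interventions are used". The third gives the baseline and the result: "Assuming a 37% incidence of PDNV based on previous literature", and then "to be powered to find a 20% reduction in risk from baseline the study must include 140 patients".

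Section 5d treats 140 as the total for the whole study: "it will take approximately five years to enroll the necessary 140 patients". It also gives the pace: "we expect to have 20-30 patients complete the study per year". The primary comparison in 5e is between two proportions: "Compare the rate of post-discharge retching/vomiting or nausea in patients who receive olanzapine versus placebo".

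Section 2 (Background) reports one small surgical trial of olanzapine. In it 57% of placebo patients needed rescue antiemetics, while "37% of patients who received 10mg of oral olanzapine required breakthrough medication". That is a 20-point difference, but on a different endpoint, and 5c does not refer to it.

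Section 5c does not say whether the 20% is relative or absolute. It gives no target rate for the olanzapine arm and no alpha, sidedness, power, test or allocation ratio. The text under 5h was not available for this review, so some of these items may be stated there.

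**The concern.** A 20% reduction in risk from a named baseline of 37% ordinarily means 20% of 37%, a fall of 7.4 points to 29.6%. A fall of 20 points to 17% is a different effect: 20/37 = 54% of the baseline risk removed. The two readings differ by a factor of about eight in sample size, and only one of them can lead to 140.

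This affects how the primary result will be read. A reader who takes 5c at face value would treat a non-significant result as evidence against a 20% risk reduction. If the true effect were a 20% relative reduction, the trial would miss it about 85% of the time with a two-sided 5% test, or 76% with a one-sided one. What 140 patients can reliably detect is roughly a halving of the rate.

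**Working it through.** **Inputs.** From 5c: control rate p1 = 0.37 and total 140. Assumed, because the available text does not state them: 1:1 allocation (n = 70 per arm), a 5% level taken both one- and two-sided, 80% as the reference power, and no dropout.

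**Formulas** (pooled two-proportion test), with p̄ = (p1 + p2)/2, S0 = √[2p̄(1 − p̄)], S1 = √[p1(1 − p1) + p2(1 − p2)]:

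- n per arm = (z_α·S0 + z_β·S1)² / (p1 − p2)²
- power = Φ{[(p1 − p2)√n − z_α·S0] / S1}
- z_α = 1.960 (two-sided 5%) or 1.645 (one-sided 5%); z_β = 0.842 for 80% power

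**Step 1: trying to reproduce 140.**

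| Reading | Test at 5% | Total for 80% power | With continuity correction |
|---|---|---|---|
| 37% to 29.6% (relative) | two-sided | 2 × 636 = 1,272 | 1,326 |
| 37% to 29.6% (relative) | one-sided | 2 × 501 = 1,002 | 1,056 |
| 37% to 17% (absolute) | two-sided | 2 × 77 = 154 | 172 |
| 37% to 17% (absolute) | one-sided | 2 × 60 = 120 | 140 |

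On the absolute reading 140 comes out exactly at one-sided 5% with 80% power and continuity correction. It also comes out at one-sided 5% with 85% power uncorrected, and at two-sided 5% with 70% power corrected. On the relative reading the required total is 1,272/140 = 9.1 or 1,002/140 = 7.2 times the plan.

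**Step 2: power at 70 per arm.**

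- Relative: S0 = 0.6665, S1 = 0.6644, 0.074 × √70 = 0.6191. Two-sided: (0.6191 − 1.960 × 0.6665)/0.6644 = −1.034, power 15%. One-sided: −0.718, power 24%.
- Absolute: S0 = 0.6279, S1 = 0.6117, 0.20 × √70 = 1.6733. Two-sided: (1.6733 − 1.960 × 0.6279)/0.6117 = 0.724, power 77%. One-sided: 1.047, power 85%.
- Fisher's exact test gives 12% and 18% (relative), 71% and 81% (absolute).

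**Step 3: do other settings rescue the relative reading?** At one-sided 10%, 80% power needs 730 patients and 70% power still needs 530. Taking 140 as the number per arm, against 5d, gives only 26% (two-sided 5%) or 37% (one-sided 5%).

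**Step 4: what 70 per arm can detect.** Solving for 80% power from 37% gives 16.3% two-sided (20.7 points, 56% relative) or 18.3% one-sided (18.7 points, 50% relative).

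**Step 5: what a result would look like.** The 95% CI half-width for the risk difference, 1.96 × S1/√70, is 16.0 points at 37% vs 37%, 15.6 at 37% vs 29.6%, and 14.3 at 37% vs 17%. As an example close to a 20% relative reduction, take 26/70 on placebo and 21/70 on olanzapine. Then z = 0.895, two-sided p = 0.37, and the difference is −7.1 points with 95% CI −22.7 to +8.5. That interval contains both no effect and a 20-point benefit.

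**The case against.** The strongest reply is that an absolute effect was meant and loosely described. The sentence in 5c calling the reduction additive supports this: percentage-point effects add, whereas independent relative reductions would normally multiply. The 57% vs 37% result in Section 2 is a 20-point gap, and 140 is reproduced exactly for a 20-point fall under some ordinary settings. On this view the trial is not several times too small, and leading with 15% power emphasises the less likely intention.

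Much of this stands. An absolute effect may well have been used, and 140 is not shown to be wrong on that reading. But these are hints. Section 5c never mentions percentage points or a 17% target, and the Section 2 result concerns rescue medication use, not the primary endpoint. Even on the absolute reading, two-sided 5% with 80% power needs 154 patients (172 corrected), so the justification is incomplete without alpha and sidedness.

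A second reply is that the text under 5h may give the missing parameters. That is possible, and their absence is not asserted here. A statement there that the effect is absolute would settle the intent, though 5c would still need matching words. No usual alpha or power stated there could make 140 fit the relative reading.

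A third reply is that no available section says a null result would be taken to rule out a 20% reduction. That is correct: the harm is the misreading that the wording invites, not a planned inference.

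**Conclusion.** The concern holds. As worded, the effect in 5c and the number 140 do not belong together: power is about 15% (two-sided 5%) or 24% (one-sided 5%), and the required total is roughly 7 to 9 times larger. The number fits only a fall from 37% to 17%, with about 77% or 85% power.

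The exact figures rest on 1:1 allocation, a 5% level and no dropout, all assumed. The mismatch itself does not depend on those levels, since it persisted over every alpha from 2.5% to 10%, one- or two-sided, and every power from 70% to 90% tried. This is a conflict between the wording and the number, not proof that 140 was miscalculated. It should be corrected before unblinding because it determines what a null primary result can be said to exclude.

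**What to change.** Keep 140 and restate 5c. Recover the original calculation first, so that the alpha, sidedness and scale entered are those actually used. Suggested text:

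> Assuming a 37% control rate and 70 patients per arm, 140 patients give [power] at [alpha, one- or two-sided] to detect an absolute reduction of 20 percentage points (37% to 17%, a 54% relative reduction). Power for a 20% relative reduction (37% to 29.6%) is about 15% at two-sided 5%, so a non-significant result does not exclude it.

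The matching power for the first sentence is about 77% at two-sided 5% or 85% at one-sided 5%. If a one-sided test was planned, the second sentence should give about 24%. If the original calculation shows that a relative effect was intended, say so, and present the 20-point figure as what 140 patients can detect, not as the original target.

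Report the primary result as a risk difference with its 95% CI (expected half-width about 14 to 16 points), unless the text under 5h already provides for this.

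The cost is protocol wording, with no extra patients. The downside is that the plan then says openly that it can reliably detect only about a halving of the rate. Resizing for the relative effect is not realistic: at 20 to 30 completers a year, 1,272 patients would take 1,272/30 = 42 to 1,272/20 = 64 years.
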